7.8 Follow-up assessments

To meet the pre-specified objectives, the following data will be collected:

Measure	Description	3 months	3 months MDC	6 months	6 months MDC
Clinical status					
Shoulder Pain	Oxford Shoulder Score (OSS); 12 items, 5 discrete responses per item	✓	✓	✓	✓
Shoulder Function	Oxford Shoulder Score (OSS); 12 items, 5 discrete responses per item	✓	✓	✓	✓
Health related quality of life	EuroQol:EQ-5D-5L	✓	✓	✓	✓
Global change measure	Via questionnaire	✓	✓	✓	✓
Time taken to return to work (if applicable)	Via questionnaire	✓		✓	
Time taken to return to driving (if applicable)	Via questionnaire	✓		✓	
Adverse events	Via questionnaire and clinician report	✓	✓	✓	✓
Trial assessments/ Process Outcomes					
Patient participant satisfaction with the interventions	Participant satisfaction with intervention using a questionnaire with 5-point ordinal satisfaction question; very satisfied/satisfied/neutral/dissatisfied/very dissatisfied	✓		✓	
Health Care Utilisation					
Health Care Resource Use (including medication use)	Health Care Resource Use Questionnaire	✓		✓	
Days lost from work (if applicable)	Days lost from work due to the shoulder problem as a component question of Health Care Resource Use Questionnaire	✓		✓	
Date treatment commenced (surgery or physiotherapist-led exercise)	Via on-site Research Health Care Practitioner				

MDC = Minimum Data Collection over the telephone

7.9 Integrated studies

Quintet Recruitment Intervention (QRI)

Surgical RCTs can be challenging to recruit to with clear obstacles including a lack of time and strong patient preferences but also hidden challenges including tensions for clinicians and challenges around assuming a position of equipoise [35,36]. However, without formal evaluation, the recruitment challenges remain unknown and opportunities to change RCT processes, for example study training and documentation, are lost to the potential detriment to the RCT. In recognition of this the QRI will be integrated with the SPeEDy RCT to understand the challenges associated with recruitment and develop action plans to address these challenges rapidly while recruitment is underway.

The QRI is a mixed-methods approach that includes data collection and analysis of screening and eligibility logs, audio-recordings of recruitment consultations (i.e. consultations during which recruitment to the RCT is discussed), individual interviews with patients and clinicians involved in recruitment, and review of study documentation as a basis for developing action plans to address identified difficulties while recruitment to the RCT is underway [36,37]. It has been shown to facilitate recruitment to the most challenging RCTs, including orthopaedic RCTs [36,38]. A targeted QRI, investigating recruiter information provision, patient responses to this information and recruitment performance across recruiters/sites, will be integrated within the recruitment period of the SPeEDy RCT over the first nine months to enable barriers to recruitment to be identified and any changes to the recruitment process to be made and re-evaluated.

Recruitment

Prior to commencement of the relevant hospital clinic, the clinician or RHCP will screen the clinic list of all clinicians at study sites who have consented to audio-recording of their clinic appointments with potentially eligible patients. Information about the QRI will be presented to the clinicians and RHCPs during the initial study site training where the purpose and process of audio recording will be explained. Clinicians will be provided with written health care professional (HCP) participant information sheets during site training visits and will be given the opportunity to consent to audio-recording of clinic and recruitment appointments and/or consent to take part in an individual interview. If clinicians consent to participate in the audio-recording aspect of the QRI, this will be recorded at site. Although we aim to collect as many audio-recordings as possible, participation in the QRI (either consent to audio recordings or interviews) is not a pre-requisite for participation in the SPeEDy RCT.

The initial screen of the clinic list will identify, as far as possible, adult patients (≥ 18 years) suspected of presenting with a traumatic tear of the rotator cuff (shoulder pain +/- weakness following a traumatic incident, e.g. a fall. This initial screen will be reviewed by the attending clinician (surgeon or physiotherapist) to confirm potential eligibility based on available details, as required.

On arrival at the orthopaedic department, prior to the clinic appointment, the clinician or RHCP will meet the patient and discuss the QRI (referred to as the 'communication study') the purpose of which is to investigate how clinicians discuss trial participation with patients. Consent to contact regarding a future interview to explore reasons for participating or not participating in the SPeEDy RCT, if eligible, will also be requested at this point. A brief Participant Information Sheet (PIS) describing the QRI will be appended to a full PIS and will be provided along with a consent form relating to consent to audio-recording and consent to contact for a future qualitative interview, if relevant. The patient will be given time to consider the brief PIS prior to their clinic appointments.

If informed consent is gained, the clinician will be informed and the patient's clinic appointments will continue with audio-recording. Audio files will be removed from the recorder at the earliest opportunity by the clinician or RHCP at site and audio files uploaded and held on NHS computers (in accordance with NHS information governance and security arrangements) and deleted from the recorder. For consenting participants (clinicians and patients), a two working day cooling off period will be offered. This will enable participants time to read the full PIS after the clinic appointment. Participants will be provided with contact details of the clinical site Principal Investigator or nominated person whom they can contact to withdraw consent and hence request that the audio recordings be deleted rather than securely sent to the research team for analysis.

If consent remains in place (for both clinician and patient participant) after the two-working day cooling off period, only then will audio files will be securely transferred via nhs.net to Keele University and saved on Keele's Secure Network.

If informed consent is not gained, clinic appointments will continue without audio-recording.

During clinic, if a diagnosis of traumatic rotator cuff tear is confirmed and the patient is eligible for surgery, then the clinician will introduce the SPeEDy RCT or record reasons for not discussing the RCT (e.g. not fit for surgery, size and/ or location of tear implies clear need for surgery in clinician's opinion, tear deemed irreparable and not surgical candidate) and routine care will continue. If the patient has been invited to join the RCT but has declined participation, routine care will continue but, where written consent has been given (described above), the patient will be invited by the clinician or RHCP to confirm consent to contact by the research team to discuss participating in an interview to explore reasons for declining. Purposive sampling will be used to include a wide range of experience, e.g. patients from different sites, patients approached by different clinicians. Interviews will explore the perspectives of the interviewees in relation to the recruitment process to identify facilitators and barriers[36].

Where participants consent to audio-recording and also are interested in participating in the SPeEDy RCT, these recruitment appointments with the clinicians and/ or RHCP will be audio-recorded where

prior consent is provided. The two working day cooling off period will also apply, for both RHCPs and patients.

Data Collection

In line with the SEAR (Screening, Eligibility, Approached, Randomised) framework [39], screening and eligibility logs will detail: patients who were screened (by RHCP and attending clinician); those eligible or ineligible along with reasons; those approached about participation, including reasons why not approached; and whether they accepted randomisation within the RCT, and if not, why not. Logs will also record which arm patients accepting randomisation are allocated to and whether they accept this allocation. These will be completed at the clinical site.

Clinic and recruitment appointments will be audio-recorded and then subjected to targeted data extraction and transcription, focusing on issues relevant to recruitment to the SPeEDy RCT. Such a targeted approach recognises that much of the recorded discussion will not primarily relate to issues around recruitment to the SPeEDy RCT and hence are unlikely to be relevant to the aim of the QRI. Audio files of these appointments will be securely transferred from Keele CTU to a professional transcription company, who are contracted under strict terms of confidentiality, via a secure portal. Transcripts will be password encrypted when being returned by email by the transcription company to Keele University. These will then be securely uploaded back onto Keele's Secure Network and the email version deleted.

In-depth, semi-structured interviews will be conducted, guided by topic guides with a purposive sample of patients, clinicians involved in identifying patients and RHCPs, (responsible for explaining the trial and obtaining informed consent) from selected sites. Selection of sites will be determined by willingness to participate in the QRI and relative recruitment performance, i.e. high and low-recruiting sites. On receipt of consent to contact, contact to discuss an interview will be made by telephone initially. Subsequently, upon receipt of written consent, the interviews will be undertaken at a time and place convenient to the interviewee and could include interviews at home, either face-to-face or telephone, or at the hospital.

Given the responsive and iterative nature of the QRI, it is not realistic to pre-specify a required number of participants. But, we will sample data from at least four out of the eight hospital sites and data collection will be limited to the pre-specified maximum nine-month period. However, data collection will cease if no new themes emerge from the ongoing analysis prior to this time point.

Data Analysis

Data from the screening and eligibility logs will be analysed descriptively to identify differences between sites and points in the recruitment pathway where patients at particular sites are 'lost' to recruitment.

Findings from this analysis will guide sampling for audio-recording of recruitment discussions and interviews.

Audio-recordings of clinic and recruitment appointments will be analysed using thematic, content and targeted conversation analysis techniques with the aim of understanding the challenges to recruitment [40]. In tandem with this, data from individual interviews will be analysed using constant comparison techniques which involves detailed coding followed by comparison of emerging themes and codes within transcripts and across the dataset looking for shared or disparate views. Findings will be presented anonymously.

Further analysis of the study documentation, including PIS and consent forms and Trial Management Group (TMG)/Trial Steering Committee (TSC) meeting minutes, will be reviewed with reference to the findings from the interviews and recruitment appointments. Data from screening logs, audio recordings, interviews and study documentation will be triangulated to identify where findings are confirmed across data sources.

Upon completion of this analysis an action plan will be generated to address the factors that appear to be hindering recruitment. Previous reports of the outcome of the QRI have identified generic and study specific barriers to recruitment which can be addressed through bespoke action plans [36]. Also in some instances the QRI has provided clear reasons why recruitment to the RCT might not be achievable [36]. Once the action-plan is agreed, where relevant, study documentation will be amended and further training offered to recruiters across all of the hospital sites. Post implementation of the plan, a further evaluation of the recruitment process will be undertaken using feasibility outcome data described in this protocol.

Further qualitative interviews

Recruitment

Following the six-month follow-up point, a further sample of patient participants will be purposively sampled from both treatment arms and interviewed to explore reasons for initial participation, treatment acceptability, reasons for non-completion of treatment, where relevant, and any reasons for treatment cross-over.

Information relating to the qualitative interviews will be included in the initial PIS for the SPeEDy RCT and consent to further contact will be included. Where consent to contact is indicated, the researcher will telephone the patient to discuss involvement in the qualitative interviews. If the patient expresses interest, then a PIS describing the qualitative interviews and a consent form will be posted to them. On receipt of a signed consent form, a mutually convenient time to undertake the interview will be agreed.

Patients will be purposefully sampled with respect to allocated group, change in pain and disability status according to the OSS, whether the allocated treatment was completed or not and in relation to treatment cross-over. Patients will be able to decline participation in the interviews yet still be involved in the RCT.

Qualitative Data Collection

The interviews will be based on semi-structured topic guides developed in relation to the pre-specified aims but also with PPIE (approximately 30-minute telephone interview).

It is expected that approximately 20 patients will be sufficient to attain rich data. Telephone interviews will be conducted, audio-recorded and transcribed ad verbatim.

Qualitative Data Analysis

Interviews will be analysed both thematically and as narratives (capturing the 'patient journey' for each participant). This analytical approach ensures that the context of individual patient journeys is preserved while undertaking a broader thematic analysis [41,42]. NVivo software will be used, enabling development of an appropriate coding strategy and coding framework in a manner which facilitates data retrieval and comparative analysis [43].

7.10 Withdrawal criteria

Participants are free to withdraw from the study at any time during participant follow-up. The local site PI, study CI and Keele CTU will make every effort to ensure that the specific wishes of any participant who wishes to withdraw consent for further involvement in the trial are defined and documented.

Participants who wish to withdraw from the treatments will have the option to still receive follow-up questionnaires, if they are willing.

7.11 End of study

The end of the RCT is defined as completion of all data are collected, including MDC and case report forms.

8 STATISTICS AND DATA ANALYSIS

8.1 Sample size calculation

Randomising 76 participants will enable the 1-sided lower 90% confidence limit for the follow up rate to be estimated within about 6% of the anticipated 80% level at six months. Further, a sample size of about 76, allowing for dropout, will be sufficient to allow precise calculation of estimates of standard deviation around the OSS for the main trial [44].

Additionally, with reference to treatment crossover of less than 25% (principal concern relates to those randomised to the physiotherapist-led exercise programme crossing over to surgery), randomising 38

participants to the physiotherapist-led exercise programme enables precise 1-sided upper confidence limits (e.g. around 8% above the desired upper level of around 15% for a 90% upper confidence limit).

8.2 Planned recruitment rate

Data from NHS Hospital sites suggests there are one to two potentially eligible patients per month per surgeon equating to four to six potentially eligible patients per month at a medium-sized sites (four surgeons). Hence, working with eight sites means that it is reasonable to expect to identify 32 potentially eligible patients per month (eight x four) and the recruitment target is six to seven participants per month across approximately eight sites; this equates to a conservative 20% participation rate. The recruitment period for the RCT will be 15 months in total to enable staged recruitment of approximately eight sites over the first three months. This will enable the last site to be open for a 12 month recruitment period.

8.3 Data analysis plan

As this is a pilot and feasibility RCT, the main analysis will focus on process outcomes, for example consent rate, retention rate, and follow-up rates. Means and confidence intervals of the OSS will be calculated in order to inform the sample size calculation for the main trial. A detailed data analysis plan will be developed and agreed by the TSC.

At the end of the study, we will review the findings and in discussion with the TSC make a recommendation about proceeding to a future main trial. The following success criteria will be used to decide on whether to proceed to developing a main trial funding application:

- i) Identification of eight recruiting sites during the pilot phase with expressions of interest from at least a further eight sites; this criterion recognises that a future main trial would likely require greater than 400 participants and thus a minimum of 20 sites recruiting over a two-year period
- ii) Recruitment rates: Consent and randomisation of 20% or more of eligible patients
- iii) Treatment cross-over less than 25% at six months in each of the two treatment arms. In a future main trial, if treatment cross-over is less than 50% at 12-months this would suggest that significant financial saving could be made while offering useful data to inform decision-making. Hence, if treatment cross-over is less than 25% at six months, with accepted limitations, this will be regarded as acceptable in the context of the upper limit of longer-term cross-over
- iv) Follow-up rates for the OSS greater than 70% at six months.

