3.3 Outcome measures/endpoints

Feasibility outcomes:

- 1) Numbers of patients screened, number eligible, number approached, number consenting, number randomised, and number accepting allocation
- 2) Numbers of participants continuing in allocated treatment
- 3) Follow-up response rates to questionnaires at three and six months post-randomisation (including Oxford Shoulder Score and EQ-5D-5L)
- 4) Data from screening logs, including reasons for not approaching potentially eligible patients to inform determination of zone of clinical equipoise
- 5) Numbers of participants receiving treatment (surgery or PT-led exercise) other than that which was allocated to determine proportion of participants who cross-over
- 6) Feasibility of recruiting participating sites and numbers of additional sites who are interested in participating in the main trial
- 7) Participant satisfaction with the interventions on a five-point ordinal scale; Very Satisfied/Satisfied/Neutral/Dissatisfied/Very Dissatisfied
- 8) Barriers and facilitators to recruitment, retention and treatment cross-over (qualitative data; audio recording and individual interviews).

Clinical outcomes:

- 1) Pain and disability assessed using the Oxford Shoulder Score (OSS) at baseline, three and six months post-randomisation by post with telephone call for minimum data collection if no response to reminder postal questionnaire
- 2) Health related quality of life assessed using the EQ-5D-5L at baseline, three and six months post-randomisation by post with telephone call for minimum data collection if no response to reminder postal questionnaire
- 3) Days lost from work due to the shoulder problem at three and six months post-randomisation via postal questionnaire
- 4) Time taken to return to driving, if applicable, via questionnaire at three and six months post-randomisation via postal questionnaire
- 5) Number and type of adverse events for up to six months post-randomisation via patient self-report questionnaire or telephone Minimal Data Collection (MDC) at three and six months and via surgeon, physiotherapist or GP report.

Self-report data relating to further health care resource use, including NHS- and private borne service and medication costs will also be collected.

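### Success criterion (i) can be passed with 16 sites, although its own rationale says the main trial needs at least 20

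*Combined protocol and SAP*

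**What the plan says.** Section 8.3 lists four success criteria for deciding whether to develop a funding application for the main trial. Criterion (i) requires "Identification of eight recruiting sites during the pilot phase with expressions of interest from at least a further eight sites". The reason follows in the same sentence: the main trial would probably need more than 400 participants, "thus a minimum of 20 sites recruiting over a two-year period".

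Section 8.2 gives the recruitment assumptions for the pilot. Potentially eligible patients are put at "four to six potentially eligible patients per month at a medium-sized sites". The calculation then takes the lower figure, eight sites with four patients each, or 32 per month. On that basis "the recruitment target is six to seven participants per month across approximately eight sites; this equates to a conservative 20% participation rate".

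Two other statements bear on the point. Section 3.3 lists as an outcome: "Feasibility of recruiting participating sites and numbers of additional sites who are interested in participating in the main trial". No threshold is attached to it. Section 8.3 also says of the Oxford Shoulder Score: "Means and confidence intervals of the OSS will be calculated in order to inform the sample size calculation for the main trial". The figure of 400 is therefore provisional.

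**The concern.** The threshold and the reason given for it disagree within one sentence. The second group of eight is additional to the first, so the criterion is met at 16 sites, while the rationale names 20 as the minimum. No other section sets a different threshold for sites or explains how 16 would become 20.

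At stake is the progression decision. Section 10.1.1 has the Trial Steering Committee (TSC) advise on a main trial by reference to these criteria. A pilot could pass criterion (i) as written and still have fewer sites than the protocol considers necessary. Eight of the 16 need only have expressed interest, so any that withdraw, or any pilot site that does not continue, would widen the gap.

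**Working it through.** **Inputs**

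- Criterion (i), section 8.3: 8 recruiting sites and at least 8 further interested sites.
- Main trial, section 8.3: more than 400 participants (400 is used below, which favours the plan), at least 20 sites, 24 months.
- Pilot target, section 8.2: 6 to 7 participants per month over about 8 sites.
- Eligible patients, section 8.2: 4 per site per month in the calculation (stated range 4 to 6), with 20% participation.
- Assumption, also favourable to the plan: every site is open for the full 24 months.

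**Site count**

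8 + 8 = 16, and 20 − 16 = 4 sites short. Reaching 20 takes 20 − 8 = 12 further sites.

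**Reproducing the plan's figure of 20**

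Rate per site-month: 6/8 = 0.75; 7/8 = 0.875; 20% of 4 = 0.80.

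Sites needed = 400 / (24 × rate):

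- at 0.75: 22.2
- at 0.80: 20.8
- at 0.875: 19.05, rounded up to 20

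Exactly 20 sites corresponds to 400 / (20 × 24) = 0.833 per site-month. That is 0.833 × 8 = 6.67 per month per eight sites, inside the planned six to seven. The 20 is therefore in line with section 8.2, and the 8 + 8 is the figure that departs from it.

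**What each number of sites would recruit in 24 months**

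| Rate per site-month | 16 sites (384 site-months) | 20 sites (480 site-months) |
|---|---|---|
| 0.75 | 288 | 360 |
| 0.80 | 307 | 384 |
| 0.875 | 336 | 420 |

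Shortfall at 16 sites: 400 − 336 = 64 (16%) to 400 − 288 = 112 (28%). Reaching 400 with 16 sites would take 400 / (16 × 0.875) = 28.6 months to 400 / (16 × 0.75) = 33.3 months.

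**Break-even for 16 sites**

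400 / 384 = 1.042 per site-month, or 8.33 per month per eight sites, above the top of the planned range. This needs 1.042 / 0.20 = 5.2 eligible patients per site per month at 20% participation, or 1.042 / 4 = 26% participation at four eligible per site.

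**Sensitivity to the number eligible**

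At 20% participation and four to six eligible per site per month, 16 sites recruit 0.8 × 384 = 307 to 1.2 × 384 = 461.

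**Cross-check from the pilot sample size**

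76 participants from eight sites, each open for 12 to 15 months, means 96 to 120 site-months and a rate of 0.79 to 0.63. At that rate 16 sites give 304 to 243 in 24 months.

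**The case against.** The best defence is that no sum in the protocol is wrong and that the criterion was never meant to equal the main-trial site count. It governs a funding application, which section 10.5 places in months 37 to 48, so more sites could be found afterwards. Eight is a floor, the main-trial size is worded as likely, and the TSC will see the actual number of interested sites because it is a reported outcome. All of this is fair and limits the weight of the point. It does not remove the mismatch: a criterion is defined by the lowest result that passes, and the text does not say that the remaining sites will be found later.

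A second objection is that 16 sites could be enough. The protocol calls 20% participation conservative, and section 7.1 cites 57% of eligible patients recruited in an orthopaedic setting with the recruitment model used here. Section 8.2 also gives one to two eligible patients per surgeon and four surgeons per site. That makes four to eight per site, wider than the four to six it then states; at eight per site and 20%, 16 sites would recruit 1.6 × 384 = 614. So the participant shortfall does depend on the scenario. But the plan is built on four per site and 20%, and on that basis it arrives at 20 sites itself.

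A third objection also stands in part: 20 sites leave little or no reserve, with 384 participants at 20% of four per site. Raising the threshold to 20 makes the sentence consistent but does not guarantee 400. That is a reason to recalculate from observed data as well.

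**Conclusion.** The concern holds. Criterion (i) returns a pass at 16 sites, four below the minimum of 20 stated in the same sentence. The gap of four rests on no assumption beyond reading the second eight as additional to the first.

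The consequence in participants, 64 to 112 below 400, assumes the section 8.2 target rate and all sites open for two years. It disappears at about 5.2 eligible patients per site per month with 20% participation, or at 26% participation with four eligible.

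This should be corrected because it is one of four pre-specified progression criteria. It has no bearing on the conduct of the pilot or on its estimates.

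**What to change.** In section 8.3, criterion (i), raise the number of further sites with expressions of interest from at least eight to at least 12, so that the floor is 8 + 12 = 20.

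Add one sentence stating that, at the end of the pilot, the required number of sites will be recalculated as:

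> revised main-trial sample size / (24 × observed participants per open site-month)

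The revised sample size should be used and not a fixed 400, since the pilot Oxford Shoulder Score data are meant to inform it. For illustration, with 400 participants an observed rate of 0.80 gives 20.8, so 21 sites; 0.75 gives 22.2, so 23; 1.2 gives 13.9, so 14.

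Keeping eight and explaining how the remaining four sites will be found would also resolve the contradiction, but it is the weaker choice because the rule would still pass below its stated minimum.

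The cost is a one-line change and one added sentence. The criterion becomes slightly harder to meet, and up to four more expressions of interest must be collected.
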